### 9.2.2 Eligibility criteria

#### 9.2.2.1 Inclusion criteria

- Diagnosis of hemophilia A.
- Patients previously treated for Hemophilia A.
- Patients without previous history of inhibitors or patients with previous history of inhibitors on standard prophylaxis therapy for at least 1 year prior to study entry.
- No current evidence\* of FVIII inhibitor or clinical suspicion\*\* of FVIII inhibitor.
  - \* Evidence of FVIII inhibitor as measured by the Nijmegen-modified Bethesda assay [ $<0.6$  Bethesda units (BU/mL)] or Bethesda assay [ $<1.0$  BU/mL] in 2 on consecutive samples.
  - \*\* Documented or clinical suspicion of shortened FVIII half-life ( $<6$  hours).
- Initiation of or currently on damoctocog alfa pegol with any kind of treatment modality (on-demand, prophylaxis, or intermittent prophylaxis).
- Signed informed consent/assent.

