### 9.3.1 Variables to determine the primary endpoint

The variables for primary endpoint are:

- Annualized number of reported total bleeds.
- Severity of hemophilia.
- Severity of patient bleeding profile.
- Disease characteristics
- Prophylaxis regimen.
- Age.
- Previous exposure to damoctocog alfa pegol (i.e. naïve vs. non-naïve).

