## 9.7 Data analysis

### 9.7.1 Statistical considerations

Statistical analyses will be of an explorative and descriptive nature. The study is not aimed to confirm or reject predefined hypotheses, hence no formal hypothesis testing will be performed.

Statistical analysis of the HEM-POWR sub-study will be mostly of exploratory nature, descriptive statistics can also be applied, and will be in the statistical section of the sub-study protocol.

All variables will be analyzed descriptively with appropriate statistical methods: categorical variables by frequency tables (absolute and relative frequencies) and continuous variables by sample statistics (i.e., mean, standard deviation [SD], minimum, median, quartiles, and maximum). Continuous variables will be described by absolute value and as change from baseline per analysis time point, if applicable.

All analyses will be performed for the total study population (overall analysis). Separate analyses for individual participating countries or regions will be provided if required for local reasons when sufficient data is available.

Sample size and disposition information including reasons for discontinuation by analysis time point will be displayed in a frequency table.

All therapies documented in the following forms will be coded using the World Health Organization Drug Global.

- Prior and concomitant medication
- Prior FVII treatment

Any diagnoses/diseases/event terms documented in the following forms will be coded using the latest Medical Dictionary for Regulatory Activities (MedDRA) version:

- General medical/surgical history
- Surgeries
- Adverse events

Annual analyses are planned to provide annual safety reports and preliminary results to support publications. The final analysis will be performed after end of the study, which is the date the analytical dataset is completely available.

All statistical details including calculated variables and proposed format and content of tables will be detailed in the Statistical Analysis Plan (SAP). Bayer AG will provide oversight of data analysis activities that will be assigned to a CRO. All specific processes and technical details will be documented by the CRO statistician in the SAP and tables specification manual. The SAP will be finalized before the first database lock. The SAP is available upon request (see [Table 6](#)).

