### **Sub-populations:**

Data will be stratified by prophylaxis dosing regimen (following approved local label, see Section 9.7.3), severity of hemophilia (mild, moderate, or severe), severity of patient bleeding profile at baseline (ABR in the last 12 months prior to enrollment), medical history (in particular joint status [affected joint: yes/no; 1 affected joint/>1 affected joint]), age groups, and time on treatment (i.e., damoctocog alfa pegol-naive or not). The prophylaxis-dosing regimen as prescribed by the physician at the beginning of the study will be used for stratification, unless otherwise stated.

Assignment of patients into treatment categories in case of changes to the regimen or switch to on-demand will be specified within SAP. Whenever reasonable, further subgroups (e.g., sex, baseline patient/disease/pre-treatment characteristics) will be specified in the SAP. Selected tables (including safety events, treatment administration and prophylaxis regimen) will be presented by history of inhibitors and exposure days (to FVIII product) at baseline.

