### **9.7.2 Analysis of demography, disease details, prior and concomitant medication/treatment, and other baseline data**

Demographics and baseline disease characteristics will be described by frequency tables or summary statistics. Baseline disease characteristics will include the most recent FVIII product used prior to the start of damoctocog alfa pegol treatment. Some continuous variables will be categorized and presented in frequency tables in addition to summary statistics. Categories will be defined in the SAP.

Number of bleeds prior to enrollment (or first administration of the study drug, for damoctocog alfa pegol non-naïve patients) into the study will be summarized.

Prior and concomitant medication/treatment and medical history will be presented by frequency tables or summary statistics.

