### **9.7.3 Analysis of treatment exposure**

Analysis of treatment exposure will be performed on the SAF.

In this study, the following 4 types of exposure based on physician's prescription will be considered:

- Prophylaxis: twice weekly (including any prescription more than 7 times per month).
- Prophylaxis: every 5 days (including any prescription between >5-7 times per month).
- Other: if not listed above.
- All.

The damoctocog alfa pegol exposure will start with the first infusion in the study. The period of continuous exposure per treatment pattern (following approved local label), stops whenever prescribed damoctocog alfa pegol treatment regimen changes. Treatment patterns for non-naïve patients will also be summarized.

Exposure duration (in days) will be analyzed descriptively by summary statistics and frequency tables per treatment pattern.

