#### **ABR:**

Summary statistics of the number, type, location, and severity of reported bleeds (total, spontaneous, joint, and trauma) will be presented.

The primary analysis on ABR will be performed in patients receiving prophylactic treatment. ABRs will first be characterized using descriptive statistics by calculating mean ( $\pm$  standard deviation [SD]), median, minimum, and maximum. Further, the mean ABRs along with 95% CIs will be estimated using a negative binomial regression model corrected for over-dispersion, and with relevant treatment and disease characteristics as covariates and observed prophylactic treatment period as an offset variable.

When enough data is collected, additional analyses include: 1) comparing the ABR in patients receiving prophylactic treatment with those who are not treated with standard prophylaxis; 2) comparing the ABR in patients receiving damoctocog alfa pegol prophylactic treatment with the ABR prior to the damoctocog alfa pegol treatment.

Further details of the analysis will be described in the SAP.

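### The before/after ABR comparison is not limited to new starters; pooled with current users it can show a fall in bleeding that comes from selective persistence

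*Protocol*

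**What the plan says.** All references are to the protocol.

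- **Who enters.** Section 9.2.2.1 admits patients on "Initiation of or currently on damoctocog alfa pegol with any kind of treatment modality".
- **The comparison.** Section 9.7.4 (ABR) introduces it with "When enough data is collected, additional analyses include" and then lists "comparing the ABR in patients receiving damoctocog alfa pegol prophylactic treatment with the ABR prior to the damoctocog alfa pegol treatment". It names no restriction to new starters. Section 9.1.2 adds two related secondary endpoints: bleed counts against previous FVIII products, and the difference in bleed-free proportion against previous prophylaxis. Neither is restricted.
- **Default population.** Section 9.7.1: "All analyses will be performed for the total study population (overall analysis").
- **On-drug side.** Section 9.7.3: "The damoctocog alfa pegol exposure will start with the first infusion in the study".
- **Pre-drug side.** Sections 9.3.2 and 9.3.4 look back up to 12 months from the start of therapy. Section 9.7.2 likewise takes bleeds before enrollment "or first administration of the study drug, for damoctocog alfa pegol" non-naive patients. The count endpoint in 9.1.2 instead dates its 12 months from enrollment.
- **Prior exposure.** Section 9.3.1 lists "Previous exposure to damoctocog alfa pegol (i.e. naïve vs. non-naïve") among the primary-endpoint variables. The sub-populations paragraph of 9.7.1 stratifies by "time on treatment (i.e., damoctocog alfa pegol-naive or not"), and the objectives in the front table say the same without condition. Section 9.7.4 makes subgroup analysis of the primary outcome depend on need and on data.

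**The concern.** For a new starter the two periods adjoin: the year before the first dose, then time on the drug. For a current user there is a gap between them. With the look-back set at treatment start, bleeds between the first-ever dose and the first in-study infusion belong to neither period. Patients who did worse in that gap and stopped could not enroll as current users. The later period is conditional on having stayed on the drug, whereas the earlier period was lived before that selection took place.

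Moving the look-back to treatment start, as 9.7.2 does, keeps on-drug time out of the earlier period but leaves the selection in place. Adjustment for baseline covariates does not remove it either, because the selection acts through on-drug bleeding that these analyses do not use.

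At stake is how a change from previous treatment will be read. Section 7.2 says the results can be used to educate patients, payors and providers, and a lower ABR than on the previous product is easily quoted as the effect of switching.

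**Working it through.** **The plan's own figure.** The protocol gives no figure for this comparison. Its nearest is Table 4, the precision of mean ABR. From 9.5: 200 × (1 − 0.10) = 180 patients, μ = 6, θ = 1. The log-link negative binomial half width is μ·sinh(1.96·√((1/μ + 1/θ)/n)):

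- n = 36: 2.16 (stated 2.17)
- n = 108: 1.23 (stated 1.23)
- n = 180: 0.95 (stated 0.96)

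The planning inputs therefore reproduce and can be reused.

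**First check: leave after worsening.** Assumed, because the protocol gives none of it: no average treatment effect (true ratio 1.00); current users have one uncounted on-drug year; a patient whose first on-drug year is worse than the year before leaves with probability 0.25 or 0.50.

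- λ ~ Gamma with mean μ = 4 or 6, dispersion 1
- y0 ~ Poisson(λ) before the drug
- y1, y2 ~ Poisson(λ·e), with E[e] = 1
- leave if y1 > y0, with the stated probability
- apparent ratio = mean(y2)/mean(y0) among those who stay

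| Group | Apparent after/before ratio |
|---|---|
| Current users, same effect in all | 0.93-0.97 |
| Current users, effect varies (log SD 0.3-0.7) | 0.83-0.96 |
| 50:50 pool with new starters | 0.914-0.987 |
| New starters, first on-drug year | 1.00 |

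The spurious fall is 1 − 0.97 = 3% to 1 − 0.83 = 17% in current users. Pooled, it is 1 − 0.987 = 1.3% to 1 − 0.914 = 8.6%, or about 1-9%. Even with a uniform effect there is some fall: patients who look worse often had a low y0 by chance, so removing them raises the pre-drug mean of those who remain.

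**Second check: a different persistence rule.** μ = 6, θ = 1, true ratio 1.00, and a staying probability of 0.95 unless bleeding rose.

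| Persistence | 25% current users | 50% | 75% | 100% |
|---|---|---|---|---|
| 0.6 after worsening, log SD 0.5 | 0.98 | 0.955 | 0.93 | 0.91 |
| 0.4 after worsening, log SD 0.7 | 0.95 | 0.90 | 0.85 | 0.80 |
| 0.8 after worsening, log SD 0.3 | – | 0.99 | – | – |
| Unrelated to bleeding | 1.00 | 1.00 | 1.00 | 1.00 |

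In the first row at 50%, ABR is 6.04 before and 5.77 after: 5.77/6.04 = 0.955.

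**When it vanishes.** If leaving depends only on the absolute count y1 and the effect is the same in everyone, the ratio is 1.00. Given λ, y0 and y2 have the same mean and neither depends on y1, so selection lowers both sides equally. With varying effects (log SD 0.5, μ = 6), selection on the absolute count gave 0.94 in current users.

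**Does restricting to new starters cure it?** Section 9.2.7 ends observation at a permanent stop, and 9.7.1 keeps partly followed patients in the FAS. Applying the first leaving rule to new starters after year 1 of 3 gives a person-time ratio of 0.91-0.99 and a mean of individual ABRs 1.01-1.04 times the pre-drug mean. The person-time ratio for current users over three years is 0.77-0.97. If starting is assumed twice as likely after an above-average bleeding year, new starters alone show 0.95-0.97 in year 1, from regression to the mean.

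**Cost in precision.** The same half-width formula gives 1.10, 1.35 and 1.93 for n = 135, 90 and 45, that is, 25%, 50% and 75% current users out of 180. At 50%: 1.35/0.95 = 1.42, close to √2. This is the precision of a one-period mean, used here as a guide to the before/after estimate.

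**The case against.** The strongest reply is that the separation is already planned and the rest belongs to the SAP. Naive status is a primary-endpoint variable, and stratification by it is stated without condition in the front table and in 9.7.1. Section 9.7.1 also uses time on treatment to define sub-populations for the main analysis. Section 9.7.4 leaves further detail to the SAP, the comparison is an additional descriptive one without a test, and 9.9 acknowledges selection bias.

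Much of this stands. A reader might infer that the protocol overlooks prior exposure, and it does not. What remains is that the protocol itself fixes mixed entry, an in-study exposure start and an overall analysis by default. It does not say which group carries the before/after result, and for the primary outcome it makes subgroup analysis optional. Section 9.9 names selection bias only in general terms.

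Three stronger readings also fail:

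- That a false fall will occur. It needs persistence to depend on bleeding in a way linked to individual change, and the documents give no stopping rates, no time on drug before enrollment and no share of current users.
- That this is the only within-patient effectiveness comparison. Section 9.1.2 also lists change in HJHS and in affected joints, besides the bleed counts and bleed-free proportion.
- That restricting to new starters removes the bias. The three-year check shows that it does not.

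**Conclusion.** The point holds as a weakness in how a secondary, descriptive comparison is set up. It is not a flaw in the primary ABR estimate. As written, the pooled before/after change mixes a contrast in new starters with one in patients already selected for staying on the drug. Under the persistence rules examined, the distortion favours the product or is nil.

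The size rests wholly on assumptions: about 3-17% in current users and 1-9% in a 50:50 pool for leaving probabilities of 25-50% after worsening, and 0% to about 10% at a 50% share across the wider set of persistence rules. A first-year comparison in new starters is free of this particular selection. A full-period one is less affected than the same comparison in current users, but not free of it.

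**What to change.** In 9.7.4, and for the two related endpoints in 9.1.2:

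- Make the damoctocog-naive stratum, from first dose, the main before/after result for ABR, bleed counts and bleed-free proportion.
- Show current users separately, with time since drug start, as a description of patients who persisted.
- Do not present the pooled change as the effect of the product.
- Report the first on-drug year, or each year, beside the full-period estimate, with the number who stopped.

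Naive status and the treatment start date are already collected (9.3.1, 9.3.7), so this needs wording and no new data. The price is precision, with a confidence interval about 1.4 times wider if half are naive. Some bias from in-study stopping and regression to the mean will remain and should be stated with the result.

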**Patients with 0 bleeding events:**

The proportions of bleed-free patients and 95% CIs for the proportions will be presented.

**Surgeries and Hemostasis during Surgeries :**

Frequencies of type and classification of surgeries, number of patients having had surgeries, FVIII treatment other than damoctocog alfa pegol (product, number of infusions, consumptions) used during surgeries, as well as hemostasis (number of infusions, FVIII consumptions) will be summarized descriptively.

**Affected joints:**

Number and location of affected joints will be summarized descriptively. Change from baseline will be evaluated at end of the study for affected joints.

**Joint health:**

Joint health will be assessed by HJHS and summarized descriptively. Change from baseline will be evaluated at end of the study for HJHS.

Joint ultrasonography results will be done for index joints per standard clinical practice using HEAD-US methods [28]. HEAD-US scores will be summarized descriptively.

**PRO:**

See Section 9.7.6.

**9.7.5 Analysis of drug utilization variables**

Analysis of the drug utilization will be performed on the FAS, and if needed and data permits, within the subgroups defined in Section 9.7.1.

**Treatment pattern:**

Summary statistics for the prescribed treatment regimen will be provided every 12 months. The proportions of patients per treatment regimen and 95% CIs for the proportions will be presented. A shift table or diagram will be provided to present the change from baseline regimens.

The physician's determinants for initial choice of a treatment regimen will be provided in frequency tables. Changes in prescribed regimen to be evaluated with documentation in the patient diary and clinical record and reason for change will be summarized and presented using frequency tables.

**Factor consumption:**

Factor consumption will be analyzed descriptively based on the patient infusion diary, including the annualized number of infusions per patient, annualized total/average dose, and other infusion characteristics. Summary statistics and frequency tables will be provided per treatment pattern, treated bleeds, and other events (e.g., surgeries).

Sensitivity analyses will be performed in case of incomplete patient infusion diary.

### **9.7.6 Analysis of patient-reported outcomes**

Analysis of PRO will be performed on the FAS, and if needed and data permits, subgroup analysis may be performed based on the subgroups defined in Section 9.7.1.

Appropriate scores for questionnaires will be derived and changes from baseline will be analyzed by summary statistics. Patients with improved, unchanged, and worsened scores will be presented using a shift table. Further details of the analysis will be described in the SAP.

### **9.7.7 Analysis of adverse events**

The analysis described in this section will be performed on incident treatment-emergent adverse events (TEAEs) on the SAF.

An overview table displaying all TEAEs will be presented. This overview table will provide a summary on patient level:

- Any event (AE of special interest, AE, SAE, and AR).
- Maximum intensity of events.
- Events with outcome of death.
- Events leading to change of treatment regimen of study treatment.
- Events leading to discontinuation of study treatment.
- Events related to inhibitor development.

AEs will be coded using the latest version of MedDRA. A summary of TEAEs will be presented by primary System Organ Class (SOC) and Preferred Term (PT). AEs will primarily be classified by MedDRA PT. Aggregate incidences at the SOC level will be presented.

Each of the AEs of special interest will be described separately. Event rates and 95% CIs will be reported as both incidence risks and exposure-adjusted incidence rates.

Additionally, a detailed listing will be provided for AEs related to the development of an inhibitor or positive inhibitor measurements, including information on history of inhibitors.

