### **8.2 Secondary objectives**

The secondary objectives in this study are to:

- Assess the long term safety of prophylaxis with damoctocog alfa pegol in the real-world setting through the collection and analysis of adverse events (AEs) of special interest (hypersensitivity reactions, loss of drug effect, renal impairment, neurocognitive disorders,

and inhibitor development), AEs, serious adverse events (SAEs), and adverse reactions (ARs).

- Evaluate joint health (Hemophilia Joint Health Score [HJHS]).
- Collect information on affected joints at baseline and in the study.
- Assess hemostasis during surgeries during the study.
- Collect and evaluate patient-reported outcomes such as Hemophilia Treatment Satisfaction Questionnaire for adults (Hemo-SAT A), Hemophilia Quality of Life Measure for adults (Hemo-QoL-A), Hemophilia Quality of Life short form for children (Hemo-QoL-SF) and Work Productivity and Activity Impairment Scale (WPAI [+ CIQ: HS]).

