**Table 3: Tabulated overview on data collected during the study**

	Enrollment/ Initial visit	Follow up visit (including end of observation)
Eligibility Assessment (see 9.2.2)	X	
Date	X	X
Demographic data (see 9.3.3)	X	
General medical/surgical history (see 9.3.5)	X	
Disease history (see 9.3.4)	X	
Bleed history (see 9.3.1)	X	
Prior FVIII treatment history (see 9.3.4)	X	
Damoctocog alfa pegol history (if any, see 9.3.7)	X	
Current prescribed damoctocog alfa pegol regimen (see 9.3.7)	X	X
Damoctocog alfa pegol dose/regimen changes, treatment switches (see 9.3.7)		X (Continuous collection)
Patient-Reported Data (Hemo-SAT A, Hemo-QoL-A, Hemo-QoL Short Form, WPAI [+ CIQ: HS]; see 9.3.10)	X	X (Month 12, 24, 36)

	Enrollment/ Initial visit	Follow up visit (including end of observation)
Physical examination (weight, height, vital signs) 	X	X
Joint Health (HJHS)	X	X
Ultrasound data 	X	X
Affected joints	X	X
Damoctocog alfa pegol Pharmacokinetic analysis  (see 9.3.7)	X	X
Concomitant medication (see 9.3.6)	X	X
Adverse events (includes systematically collected AEs and AEs of special interest (see 11)) 	X (Continuous collection)	
Inhibitor 	X	X
Patient infusion diary		X (Continuous collection)
Physician recorded bleeds 		X (Continuous collection)
Physician recorded surgeries		X (Continuous collection)
Reason for end of observation (see 9.3.11)		X (once, at occurrence)

 Routine examinations only, if available.

 PK analysis is at physician's discretion. PK testing (and the frequency of testing per the table) is part of the routine use of the product.

 Adverse events (up to 30 days after the last treatment with damoctocog alfa pegol in study period).

 Serious, life-threatening bleeds and surgery bleeds to be recorded by the physician. Physician to ask patient at each visit regarding bleeds.

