### **9.3.8 Inhibitor measurement**

Data documented by the physician, if collected, include:

- Date of measurement.
- Inhibitor test result (negative/positive).
- Titer of inhibitor (Bethesda units).

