### **Analysis populations:**

Patients who took at least 1 dose of damoctocog alfa pegol in the study will be eligible for safety analysis. The full analysis set (FAS) will include all SAF patients who have data on infusions and or bleeding events available. This will include patients who were not followed-up for 3 complete years of prophylaxis. PK analyses will be performed on the PK analysis set. The PK analysis set includes all SAF patients who have evaluable PK data.

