#### AEs of special interest:

The following AEs of special interest are reported (if done in routine clinical practice):

- Hypersensitivity reactions including skin-related and systemic reactions, such as anaphylactic reactions (seriousness should be a case-by-case decision).
- Inhibitor development: inhibitors need to be assessed as mandatory serious and reported to Bayer AG within 24 hours of awareness.
- Loss of drug effect (immune-response to PEG, anti-drug antibodies, etc.).
- Renal impairment.,
- Neurocognitive disorders.,

The reporting physician will be asked to complete additional questionnaires when any of the above AEs of special interest are reported

Any bleeding event occurring during the study will not be documented as an AE, as long as it is not considered to have a "causal relationship" to the product. The events are captured in the assessment of effectiveness. However, if the bleed requires hospitalization, it must be reported as an SAE.

The physician will be asked to document in the eCRF whether the clinical site participates in any registries whereby AEs could be reported to both the registry and the HEM-POWR study.

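### Inhibitor incidence is taken over the whole safety set although inhibitor testing is routine-only, so the rate cannot be interpreted without the number tested, and the net direction of its bias is not established

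*Protocol*

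**What the plan says.** Section 9.7.7 fixes both the population and the measures. The adverse event analysis "will be performed on incident treatment-emergent adverse events (TEAEs) on the SAF", and for the events of special interest "Event rates and 95% CIs will be reported as both incidence risks and exposure-adjusted incidence rates". Sections 8.2, 9.1.2 and 11.3 name inhibitor development as one of these events.

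Membership of the SAF is broad (Section 9.7.1, Analysis populations): "Patients who took at least 1 dose of damoctocog alfa pegol in the study will be eligible for safety analysis". The exposure risk-window in the same section limits person-years to time on prophylactic treatment. It does not limit them to time under inhibitor surveillance.

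Testing is optional throughout:
- Table 3 lists inhibitor measurement at the initial and follow-up visits, both under the footnote "Routine examinations only, if available".
- Section 9.3.8 opens its list of date, result and titre with "Data documented by the physician, if collected, include".
- Section 11.3 introduces the special-interest events with "The following AEs of special interest are reported (if done in routine clinical practice".
- Section 10.1 states that participation calls for no diagnostics or monitoring beyond usual care.

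On missing data, Section 9.7.1 says that clinical outcomes will in general not be imputed.

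**The concern.** A low-titre or silent inhibitor exists in the data only if someone tests for it. With a denominator that needs one dose and a numerator that in practice needs a test, untested patients act as observed negatives. The reported risk then depends partly on how much testing was done, and the confidence interval credits information that was never collected.

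A second mechanism works the other way. Entry requires no current evidence or suspicion of an inhibitor, but Table 3 leaves the baseline test optional. Patients already taking the product may enroll, and adverse event recording starts with the first dose after enrollment (Section 11.2). An inhibitor already present at entry but first tested later can therefore enter the analysis as incident.

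Long-term safety, with inhibitor development named, is a secondary objective of this post-authorization safety study. If few patients are tested, a low rate may reflect little testing rather than low immunogenicity, and the planned output gives the reader no means of telling the two apart.

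**Working it through.** **Inputs from the protocol.** SAF of about 200 (Section 9.5); underlying risk of 2.0%, the highest column of Table 5; SAF denominator (Section 9.7.7); optional testing (Table 3, Sections 9.3.8 and 11.3).

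**Assumed input.** The share tested, t, is not given. It is varied from 25% to 100%.

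**Step 1: reproduce the plan's figure.** Table 5 is an exact binomial tail, P(X ≥ r) with X ~ Bin(n, p). For n = 200, p = 0.02 and r = 3 this gives 0.7649, against the stated 76.5%. All 16 cells reproduce to rounding. The calculation takes every event among the 200 patients as observed.

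**Step 2: partial testing, worst case.** Suppose testing is independent of inhibitor status and an untested inhibitor is never found. The expected reported risk in the SAF is then p × t, and the chance of at least r cases is P(X ≥ r) with X ~ Bin(200, p × t). With p = 2.0%:

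| Share tested | Reported risk | At least 1 case | At least 3 cases |
|---|---|---|---|
| 100% | 2.0% | 0.982 | 0.765 |
| 75% | 1.5% | 0.951 | 0.579 |
| 50% | 1.0% | 0.866 | 0.323 |
| 25% | 0.5% | 0.633 | 0.080 |

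These probabilities are the n = 200 rows of Table 5, read at the 2.0%, 1.5%, 1.0% and 0.5% columns.

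**Step 3: width of the interval.** With no cases, the upper limit of the exact two-sided 95% interval is 1 − 0.025^(1/n).
- n = 200: 1.83%
- n = 150: 2.43%
- n = 100: 3.62%
- n = 50: 7.11%

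With two cases, 2/200 = 1.0% (0.12% to 3.57%). If only 100 were tested, 2/100 = 2.0% (0.24% to 7.04%).

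**Step 4: prevalent inhibitors.** The protocol gives no figure for inhibitors present but undetected at entry, so this upward effect cannot be sized. It cannot be netted against Step 2.

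**Step 5: comparison within the protocol.** PK measurements are optional under the same Table 3 footnote. Section 9.7.1 gives them their own analysis set, restricted to SAF patients with evaluable PK data. Inhibitor results have no such set.

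**The case against.** **Details belong to the SAP.** Section 9.7.1 sends table content and missing-data methods to the SAP and promises a description of the extent of missing data. A tested-patient table would be ordinary SAP content. That is fair as far as it goes, but the population is not left open: Section 9.7.7 names the SAF, and an SAP that follows it inherits the problem.

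**The protocol never calls untested patients negative.** This is correct. The effect is inferred from the SAF denominator, optional testing and the general absence of imputation. The inference holds because nothing removes an untested patient from the denominator.

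**Inhibitors that matter would be found.** Section 11.3 makes every inhibitor a serious event to be reported within 24 hours, and loss of drug effect is a special-interest event that could raise suspicion. This stands. The scaling in Step 2 is a worst case that fits silent or low-titre inhibitors best.

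**Safeguards exist.** Section 9.7.7 restricts the analysis to incident events and adds a listing of inhibitor events and positive results with inhibitor history. Section 9.7.1 presents selected safety tables by inhibitor history. Section 9.9 acknowledges information bias and local differences in reporting. None of these gives the number tested or the number with a negative baseline test.

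**Entry status may be tested.** The footnote in Section 9.2.2.1 refers to Bethesda assays on two consecutive samples. However, it attaches below-threshold values to evidence of an inhibitor, which read as negative results. That wording needs to be reconciled. With the test optional in Table 3 and no extra diagnostics required by Section 10.1, the better reading is that no negative test is needed.

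**A stronger reading.** A reader might infer that the inhibitor rate is biased low overall, or that the chance of at least three cases really drops from 76.5% to 32.3%. The documents support neither. The two mechanisms oppose each other, the share tested is unknown, and Table 5 concerns a generic rare event rather than inhibitors.

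**Conclusion.** The point holds in a limited form. As written, Section 9.7.7 puts never-tested patients into the denominator and person-time of the inhibitor risk and rate. For inhibitors that are not clinically evident this pulls the estimate down and makes the interval too narrow. Undetected prevalent inhibitors can push it up. The net direction is not established.

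The possible size ranges from nothing, if everyone is tested, to a reported risk of about 0.5% for a true 2.0% with a quarter tested. The lower end rests on the two worst-case assumptions of Step 2. The effect on the interval is plainest with no cases: an upper limit of 1.8% on 200 patients, against 3.6% if 100 were tested.

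Inhibitor development is one of five special-interest events under a secondary objective, so the primary bleeding-rate analysis is untouched. The change is nevertheless worth making, because without the number tested the planned rate cannot be interpreted.

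**What to change.** In Section 9.7.7:

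- Keep the SAF-based inhibitor risk and rate, labelled as such. Show beside them the number of patients with a baseline test and the number with at least one post-baseline test.
- Add an inhibitor risk and rate in one at-risk set used for both numerator and denominator: SAF patients with a documented negative test at or before baseline and at least one post-baseline test. Person-time ends at the first positive test or the last test.
- List separately any positives without a negative baseline test.
- State that the tested-set figure may be high if testing is prompted by suspicion. Do not claim that the two figures bracket the true risk: the SAF figure may contain prevalent inhibitors, so it is not a lower bound.

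The two parts of the fraction must match. Suppose, for illustration, that 100 patients are tested later, 50 of them have a negative baseline test, and the true risk is 2%. Counting cases only among the 50 gives 50 × 0.02 = 1 expected case. Over all 100 that is 1.0%; over the 50 it is 2.0%.

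The cost is protocol and SAP wording and one extra table. Section 9.3.8 already provides for test dates and results, and no additional testing is needed. The downside is a smaller denominator and a wider interval.
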